12.6 Comparisons of Outcomes that are Dependent on BM Data

1) Frequency and incidence of increased BM reticulin and/or BM fibrosis with associated clinical signs⁵, confirmed by findings in a BM biopsy and 2) frequency and incidence of collagen fibrosis with associated clinical signs confirmed by findings in BM biopsies will be analyzed between the Exposed Cohort and Unexposed Cohort in all adults with chronic ITP:

⁵ Clinical signs: any of the following: splenomegaly, hepatomegaly, leukocytosis, and cytopenia.

- Since the sample size could be very small, the detailed description of each identified case will be listed in the report.
- If there is a sufficient sample size, a formal statistical analytic comparison, as described in [Section 12.4](#), will be conducted.

Description of prevalence rate of reticulin and collagen formation among chronic ITP patients:

- This analysis will be conducted based upon all eligible adult chronic ITP patients in the period prior to romiplostim treatment by splenectomy status. Only initial BM results will be used in the analysis to reduce potential selection bias caused by repeated testing for BM with abnormal findings.
- Prevalence of patients with reticulin and collagen formation in BM will be assessed. No comparison will be conducted; however, the descriptive analysis will be used to describe demographic characteristics, clinical features, and laboratory findings.

1) Frequency and incidence of chronic idiopathic myelofibrosis (primary myelofibrosis) according to the WHO diagnostic criteria, and 2) overall and specific incidence rates of BM fibrosis findings, including reticulin and collagen fiber content formation, and chronic idiopathic myelofibrosis in the Exposed Cohort and Unexposed Cohort in adult chronic ITP patients who have BM data prior to and post romiplostim therapy:

- Since the sample size could be very small for these outcomes, the detailed description of each identified case will be listed in the report.
- If there is a sufficient sample size (e.g., approximately 10 per treatment group for each covariate considered), a formal statistical analytic comparison, as described in [Section 12.4](#), will be conducted.

2) Association of splenomegaly and/or hepatomegaly with BM fibrosis and 2) association of changes in peripheral blood prior to and following the finding of reticulin and collagen fiber content or formation (reticulin grading 1 to 3):

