- The association tests will be based on data 3 to 6 months prior to, 0 to 3 months prior to, 0 to 3 months post, and 3 to 6 months post-positive findings in BM biopsies.
- 2XN tabulation will be created and chi-square tests for categorical variables will be used to test the association.
- Multiple regression and logistic analysis will be used to investigate romiplostim's effect after adjusting for other confounders, if feasible.

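### Protocol Section 12.6 prescribes chi-square tests for associations with marrow findings without any small-count condition, so a sparse table could put a misleading p-value into a safety report

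*Protocol*

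**What the plan says.** The last block of Protocol Section 12.6 names two associations. One is "Association of splenomegaly and/or hepatomegaly with BM fibrosis". The other is change in peripheral blood before and after a reticulin or collagen finding, with reticulin graded 1 to 3. On timing it says "The association tests will be based on data 3 to 6 months prior to, 0 to 3 months prior to, 0 to 3 months post", followed by a fourth window three to six months afterwards. On method it says "2XN tabulation will be created and chi-square tests for categorical variables will be used to test the association".

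The other comparative analyses in the section are guarded:

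- For marrow findings with clinical signs: "Since the sample size could be very small, the detailed description of each identified case will be listed in the report". A formal comparison follows only if numbers suffice.
- For primary myelofibrosis and marrow fibrosis overall: "Since the sample size could be very small for these outcomes, the detailed description of each identified case will be listed in the report". Then: "If there is a sufficient sample size (e.g., approximately 10 per treatment group for each covariate considered), a formal statistical analytic comparison".
- For the regression that follows the chi-square tests: "Multiple regression and logistic analysis will be used to investigate romiplostim's effect after adjusting for other confounders, if feasible".

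The chi-square sentence carries no condition of this kind. Section 5.3 adds that marrow biopsies are not routine in ITP, so the tables rest on a subset of the cohort.

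**The concern.** Pearson's chi-square p-value is a large-sample approximation. When few patients have the marrow finding and few have the sign, the expected count in the critical cell falls far below 1 and the approximation fails, mostly by making p too small. One patient with both features can then look like strong evidence.

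The results go to the regulator every year, and Section 3.1 provides for an urgent ad hoc report if a significant risk is seen. A p-value near 0.001 that rests on one patient would be a poor input to that judgement. The opposite error is possible too: without a stated version of the test, the same table could be reported as unremarkable.

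**Working it through.** **The plan's own figure.** The protocol gives no number of positive biopsies, no sign prevalence, no alpha and no p-value for these tests, so there is nothing to reproduce. The only sizes available are the projected cohorts in Section 3.5, 623 exposed and 1860 unexposed, together 2483. Because biopsies are not routine, 2483 is a ceiling. The group sizes and prevalences below are my assumptions, as is a two-sided 0.05 level. I worked 2x2 tables only.

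**One case, 1 of 10 positives against 0 of 100 negatives.**

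- Expected count in the critical cell: 10 × 1/110 = 0.09.
- Pearson: 110 × (1×100 − 0×9)² / (10 × 100 × 1 × 109) = 10.09, p = 0.0015.
- Yates: 110 × (100 − 55)² / 109,000 = 2.04, p = 0.15.
- Fisher: 10/110 = 0.091.
- Mid-p: half of that, 0.045.

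For 1 of 5 against 0 of 50 the results are almost the same: 0.0014, 0.15, 0.091 and 0.045.

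**One case at the cohort ceiling (2483 patients).**

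| Positives | Patients with sign | Expected | Pearson p | Yates p | Fisher p |
|---|---|---|---|---|---|
| 5 | 25 (1%) | 0.05 | 0.00002 | 0.044 | 0.049 |
| 10 | 25 (1%) | 0.10 | 0.0043 | 0.21 | 0.096 |
| 10 | 50 (2%) | 0.20 | 0.072 | 0.50 | 0.18 |
| 20 | 25 (1%) | 0.20 | 0.073 | 0.50 | 0.18 |
| 5 | 124 (5%) | 0.25 | 0.12 | 0.61 | 0.23 |

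The small p-values disappear as the sign becomes commoner or the positives more numerous.

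**Actual size of the nominal 5% test.** I summed the binomial probabilities of every table that rejects when the sign is equally common in both groups. For 10 against 100 at 2%, Pearson rejects in these cases:

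- One sign among the positives and at most one among the negatives: 0.1667 × 0.4033 = 0.067.
- Two among the positives and at most four among the negatives: 0.0153 × 0.949 = 0.0145.
- Three or more among the positives: about 0.0008.

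The total is about 0.083, most of it from tables with one positive case. The same sum in other settings gives:

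| Positives v negatives | Sign | Pearson | Yates | Fisher | Mid-p |
|---|---|---|---|---|---|
| 3 v 50 | 1% | 2.9% | 0.0% | 0.0% | 1.8% |
| 5 v 50 | 3% | 8.2% | 0.7% | 0.7% | 3.7% |
| 10 v 100 | 2% | 8.3% | 1.1% | 1.1% | 3.6% |
| 10 v 100 | 10% | 4.3% | 1.7% | 2.4% | 4.0% |
| 20 v 100 | 1% | 7.3% | 0.7% | 0.7% | 1.3% |
| 20 v 100 | 3% | 5.0% | 1.5% | 1.5% | 3.4% |
| 20 v 100 | 5% | 3.7% | 1.6% | 1.9% | 3.5% |

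**How many positives would suffice.** The expected count is roughly positives × prevalence. Reaching 5 takes about 5/0.01 = 500 positives at a 1% sign, or 5/0.05 = 100 at a 5% sign.

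**The case against.** The strongest reply is that this is detail for the statistical analysis plan. The protocol foresees one, and a single line naming a test family need not mean the uncorrected version or rule out an exact one. That stands in part. A missing fallback alone would be no finding, and with Yates' correction the 10 v 100 example gives 0.15. What remains is that the sentence is unconditional where its neighbours are guarded, and that one table can yield 0.0015 or 0.15 depending on a version the protocol does not state.

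A reader might infer that the section expects very small numbers for these association tests. It does not say so. Both warnings are attached to incidence comparisons between cohorts. The association block covers any reticulin finding of grade 1 to 3, and Section 5.5 draws on all patients with a stained biopsy, so there may be more positives. Nor do the documents make blood changes rare in these patients. Still, the marrow findings overlap, and fibrosis with an enlarged spleen or liver is where sparse tables are most plausible.

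Finally, the study is descriptive with no hypotheses (Section 2.4), fibrosis cases receive narratives, and Section 12.8 asks for caution in raising signals. This limits the harm but does not make the p-value right.

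**Conclusion.** The point holds as a minor drafting fault. A test is prescribed without the small-count condition that the surrounding text suggests it needs. Its effect depends on three things the documents do not state: an uncorrected Pearson test, about 3 to 10 positives, and a sign prevalence of about 1 to 3%. One case can then give p of about 0.001, and the size reaches about 8%, though not in every such setting (2.9% for 3 v 50 at 1%). With a 10% sign the size is below 5%. With 20 positives against 100 it is at or below 5% from a sign prevalence of about 3%, but still 7.3% at 1%.

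It would be too strong to say that the plan will declare one case highly significant. No alpha is set, and the version of the test and the counts are unknown. The harm is a misleading p-value in an exploratory safety report, with no confirmatory conclusion at risk.

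**What to change.** In Section 12.6, make the chi-square sentence conditional. When any expected count is below 5, use a mid-p or exact test for 2x2 tables and an exact or permutation test for 2xN tables, with a trend test where the columns are reticulin grades. Keep chi-square for well-filled tables. In all cases give the counts and the proportion difference or odds ratio with an exact 95% interval.

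The cost is one sentence, with no change to data, design or sample size. Replacing every chi-square test with Fisher's would go further than the problem and would lose sensitivity in a signal-detection study: its size is 0.7% to 1.1% in the two settings where Pearson's is about 8%. Mid-p limits that loss (3.6% to 3.7% there). It is not a cure for one-case tables, since it gives 0.045 for 1 of 10 against 0 of 100, so the counts and interval should be read with it.

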12.7 Stratified Analysis

Stratified analyses will be used as needed. The following are some variables to be considered as stratification factors:

- Sex and age (< 18, 18 to 30, 31 to 50, 51 to 70, and 71+)
- BMI and/or BSI
- Propensity scores (5 strata)
- Initial platelet level (< 10×10^9 , 10 to 30×10^9 , ≥ 30 to 50×10^9)
- Length of chronic ITP since diagnosis (< 1 year, 1 to 3 years, 4+ years)
- Year of initial ITP diagnosis (1996 to 2000, 2001 to 2005, 2006 to 2010, 2011 to 2015, and 2016 to 2018)
- Splenectomy (yes or no)
- Receiving immunosuppressive therapy
- Concomitant bleeding disorder/history of significant bleeding
- Any significant span of years (based on changing practice patterns)
- Country (if practice patterns differ among studied countries)

12.8 Comparison of Study Outcomes with External Data Sources

Since selection bias caused by confounding by indication for this study could be very large and some impacts are not measurable, in addition to internal comparison the study will compare the incidence rates from the romiplostim-exposed cohort to that from other potential sources where sufficient data may be present:

- Amgen Study 20080092 (Nplate™ Patient Safety Registry – Canada version)
- Amgen Study 20080045 (Nplate™ Patient Safety Registry – US version)
- Amgen Study 20070796 (Determination of Frequency Rates of Bone Marrow Fibrosis and Thrombotic/Thromboembolic Events in Patients with Chronic Immune (Idiopathic) Thrombocytopenic Purpura in Denmark)
- Administrative databases such as SEER, Ingenix, and GPRD, if appropriate data are available at time of analysis

- Published data on the frequency of predefined risks, such as [Mufti et al, 2007](#) (J Supp Oncol 2007;5(S2):80-81) and [Aledort et al, 2004](#). (Am J Hematol. 2004;76(3):205-213)
- Data available from Amgen's ongoing romiplostim clinical program

The signals and/or hypothesis will be generated based upon both internal and external comparison data, with great caution and appropriate contextualization applied.

12.9 Missing Data and Loss to Follow-up

Since this study is based on the NHRS, missing data and patients being lost to follow-up are a relatively minor issue. The study estimates that less than 5% of ITP patients will be lost to follow-up due to emigration to other countries. Since the study is able to assess all electronic medical records of study subjects, any missing data for outcomes of interest will be retrieved from medical chart reviews. Through the medical chart review, the study will distinguish missing values from those unknown or not tested. The analysis will treat missing and unknown values differently, although the study will not be able to retrieve all missing data for covariates. Appropriate approaches to missing data will be explored depending on the ascertainment of the missingness mechanism.

12.10 Analysis for Chronic ITP Patients with Renal Impairment

Since sample size could be very small, safety assessment for these renal functional impaired patients will be mainly focused on individual case description and line listing. When sample size is sufficient to conduct statistical analysis, special analyses will be conducted for chronic ITP patients with renal impairment medical conditions at the time romiplostim therapy is initiated. The analysis will include multivariate analysis and stratified analysis:

- Multivariate analysis will be used to justify for renal comorbidities and / or medical history (see [Section 12.2](#), [12.3](#), and [12.4](#)).
- Stratified analysis based on renal impairment status will be conducted to describe patient's safety profile, including incidence rate of renal failure within each renal impairment stratum. Other outcomes listed in this study proposal will also be described within each predefined stratum.

12.11 Analysis for Romiplostim Off-label Users

Analysis for romiplostim off-label users is descriptive in nature for the purpose of hypothesis generation. The analyses will describe the off-label study population in different study time periods. Analysis will include:

- Total number of subjects and total person-year observation time for all off-label users, as well as in each major underlying disease/condition cohort in the current reporting period, and cumulative for all reporting periods
- Description analysis for romiplostim-off-label utilization pattern, including
- Underlying disease for which the drug is used
- Underlying disease characteristics (eg, length, stage, and severity of underlying diseases)
- Demographic characteristics

12.12 Annual Analysis and Early Stopping Guidelines

Since this study will be used to fulfill the European regulatory agency requirements, annual assessments are planned. For each pre-specified analysis scheduled, the NCPRR investigators will conduct an annual analysis based on available data. The analysis will be limited to the analyses described in [Section 12](#). The annual analysis results will be communicated to the regulatory agency through PSURs.

There are no pre-defined early stopping rules for this study.

13. LIMITATIONS

The major limitations in the NCPRR study design are:

- The sample size is relatively small: ITP is an orphan disease and the population available for the study is limited (estimated at only 623 adult chronic ITP patients). The small sample size will limit assessment of risk for some rare events (eg, AML or MDS). To address this issue, Amgen will conduct an all patient registry in the US (US PSR) and a selected patient registry in Canada (CAN PSR), and some rare events may be effectively assessed by combining the findings of these studies.
- Limited countries are involved: The study will only include data from 3 Nordic countries, and may not represent romiplostim's benefit/risk profile of experiences for the entire European population, given that the health care system and practice patterns of ITP treatments may be different among countries. The key purpose of the study is to assess effect of romiplostim, and by creating a reasonable

comparison group such an assessment can be achieved. Amgen also plans to conduct a drug utilization study in most European countries which will provide information on how romiplostim will be used in these countries under different health care systems and practice guidelines.

- [Section 8](#) has identified four potential sources of bias in the study design. Although several methods have been considered in the study design to address these issues, it is probable the residual of these biases may still remain (eg, unmeasured selection bias due to physicians' prescribing behavior and selection bias caused by excluding patients with missing values).
- Comparability of the exposed and unexposed to reduce bias in the analysis of the outcomes may not be achieved. It is possible that propensity score adjustment will not be adequate to reduce the confounding by indication. In this scenario, caution should be taken that the comparative analyses will be inherently challenging to interpret due to the potential for bias. The context for results observed for romiplostim-treated patients should be considered in relationship to not only internal comparisons within the Nordic registry, but too other potential sources of information ([Section 12.8](#)) for establishing that context as well.

14. ETHICAL AND REGULATORY OBLIGATIONS

14.1 Informed Consent

Since the NCPRR is based upon the NHRS databases, it will not be necessary to obtain patient consent to obtain data. Study results will only be presented in an aggregate form so that individuals will not be identified.

The NCPRR may request a review of an individual patient's electronic medical records, however, as well as assessment of a patient's biological samples (eg, BM).

Communication with potential investigators of the study has confirmed that it will not be necessary to obtain informed consent from patients when detailed chart reviews and BM biopsy staining and reviews are conducted.

15. COMMUNICATION OF STUDY RESULTS

15.1 Communication of Study Results to Regulatory Agencies

The health risk findings of the registries associated with Amgen products must be reported to regulatory agencies according to local and international requirements.

Depending on the nature of the result and the regulations applied, the results may need

to be reported in an expedited manner (eg, as “new relevant safety information”). In any case, results of all registry studies of drug safety should be included in Amgen’s periodic aggregated regulatory reports, such as the PSUR and similar regulatory documents, with appropriate contextualization provided.

The NCPRR will conduct an assessment annually. The assessment results will be submitted to regulatory agencies worldwide through the PSUR.

16. ADMINISTRATIVE CONSIDERATIONS

16.1 The NCPRR International Investigator Study Team (IIST) Responsibilities

The NCPRR IIST is responsible to the NCPRR for:

- Maintaining IRB approval for the Registry study
- Developing the Statistical Analysis Plan (SAP) for the NCPRR
- The collection, management, and follow-up qualified study subjects prospectively
- Establishing and managing the Registry databases
- Compiling research data based upon the NCPRR study objectives from the NHRS
- Providing all relevant single case and aggregate clinical data, including all predefined adverse event data to Amgen and the Advisory Committee for review
- Providing data, including both individual case and cumulative data, that is specifically requested to be reviewed by the NCPRR SAC
- Collaborating with Amgen scientists to develop interim, ad hoc, and final study reports to be reviewed by the NCPRR SAC
- Being available to answer questions and facilitate requests for additional data
- Collaborating with Amgen for routine auditing
- Working with Amgen to prepare publications resulting from the Registry

16.2 Registry Coordination Center & Investigator Team Leader Responsibilities

Registry Coordination Center and Investigator Team Leader are responsible for:

- Oversight of the registry team’s responsibilities
- Ensure effective communication between Amgen and the Investigators
- Manage the service agreement between Amgen and the Investigators, and the related budget

16.3 Amgen Responsibilities

An Amgen cross functional team that consists of Global Safety Officers (GSO), Global Development Leaders (GDL), Epidemiologists from PV-Epidemiology and the Global Epidemiology team, and Safety Biostatisticians will provide scientific and technical support to the NCPRR conduct and the NCPRR SAC activities. Their representatives will participate in the NCPRR Scientific Advisory Committee (SAC) meeting. Amgen's responsibilities to the NCPRR and the NCPRR SAC are to:

- Review and approve final study design and methodologies, and study protocol finalization prior to the study initiation
- Coordinate with the IIST to develop the analysis plan before the study initiation
- Ensure that study data meets regulatory standards for data quality management and auditing
- Collaborate with IIST investigators to develop interim, ad hoc, and final study reports to be reviewed by the NCPRR
- Communicate with regulatory authorities on study design, protocol, study results and other pertinent information
- Fulfill Amgen's regulatory responsibilities, including development and submission of annual interim reports and the final study report to the regulatory agency
- Be available to answer questions and facilitate requests for additional data at the meeting, as well as outside of the meeting
- Communicate to the NCPRR SAC any decisions made concerning NCPRR SAC recommendations and notify the NCPRR SAC of all changes to the protocol or the NCPRR conduct
- Archive NCPRR SAC records (by the NCPRR SAC Liaison)
- Schedule NCPRR SAC meetings and prepare meeting agendas
- Collaborate with the IIST to prepare relevant publications.

17. APPENDICES

Appendix 1. Probability of Detecting Specified Relative Risk for Estimated Incidence Rates for the Study Sample Size

Estimated Background Incidence Rate (%)	Relative Risk				
	1.25	1.50	2.00	3.00	4.00
	Power (%)				
0.1	4	9	26	69	92
0.2	6	16	50	94	99
0.5	13	40	89	99	99
1.0	24	70	99	99	99
2.0	46	99	99	99	99
5.0	85	99	99	99	99

Appendix 2. Conditions Associated with Thrombocytopenia Other Than cITP

Diseases and Condition	ICD-10 Codes
Hereditary syndromes and Immunodeficiency:	
Alport syndrome	Q87.8
Fanconi anemia	D61.0B
May Hegglin anomaly	D72.0 (genetic abnormalities of leukocytes)
CVI (hypogammaglobulinemia)	D80.0, D80.1 (hereditary and nonfamilial hypogammaglobulinemia)
IgA deficiency	D80.2
IgG subclass 2 deficiency	D80.3
Low C4 counts	D84.1 (defects in the complement system)
Systemic "Global" autoimmunity:	
Evans syndrome and autoimmune hemolytic anemia	D69.3 & D59.0/D59.1
Systemic lupus erythematosus (SLE)	M32
Infections:	
HIV/AIDS	B20-B24
Hepatitis C	B17.1, B18.2
Lymphoproliferative disorders Malignant:	
Solid tumor	C00-C80
Hematological malignancies	C81-C96
Lymphoproliferative disorders non-Malignant:	
Autoimmune lymphoproliferative syndrome type I (ALPS) (or Canale-Smith syndrome)	D36.0 (benign neoplasms of lymph nodes)
Liver disorders:	
Diseases of liver	K70-K77
Bone marrow disorders	
Agranulocytosis	D70
Aplasia pure red cell	D60
Aplastic anaemia,pancytopenia	D61.0, D61.1, D61.2, D61.3, D61.9
Bone marrow transplant rejection	T86.0
Bone marrow tumour cell infiltration	Z94.8
Myelodysplastic syndrome	D46
Myelofibrosis	C94.5
Myeloproliferative disorder	D47.1
Other transplants, incl. bone marrow	Z94.8
Other disorders involving platelets	
Allergic purpura	D69.0
Qualitative platelet defects	D69.1
Secondary thrombocytopenia	D69.5
Antiphospholipid syndrome	D68.8 (coagulation defects)
Disseminated intravascular coagulation	D65
Hemolytic-uremic syndrome	D59.3
Thrombocytopenia neonatal	P61.0
Thrombotic thrombocytopenic purpura	M31.1
von Willebrand's disease	D68.0
Wiskott-Aldrich syndrome	D82.0

